#### 6.2.3.4. Geometric mean titers (GMTs) and concentrations (GMCs)

Geometric Mean Titer (GMT) or Concentration (GMC) calculations are performed by taking the inverse logarithm of the mean of the log titer or concentration transformations. Non quantifiable antibody titers or concentrations will be converted as described in section 6.2.3.3 for the purpose of GMT/GMC calculation. Cut-off values are defined by the laboratory before the analysis.

#### **6.2.3.5. Onset day**

The onset day for an event (e.g. AE, concomitant medication/vaccination) is the number of days between the last (i.e., most recently received) study dose (i.e., it may be dose 1 or dose 2 of the study intervention) and the start date of the event plus one day. This is 1 for an event occurring on the same day as a study dose (and reported as starting after study dose) and e.g., 2 for an event occurring on the day after the study dose was given.

#### **6.2.3.6. Duration of events**

The duration of an event with a start and end date will be the difference between the start and end date plus one day, i.e. an event that starts on 3 March 2018 and ends on 12 March 2018 has a duration of 10 days.

The duration of solicited events will be calculated as the sum of the individual days with the AE reported at grade 1 or higher during the solicited event period.

#### **6.2.3.7. Counting rules for combining solicited and unsolicited adverse events**

For output combining solicited and unsolicited AEs, all SAEs will be considered systemic events since the administration site flag is not included in the expedited AE eCRF pages. Unsolicited AEs with missing administration site flag will also be considered systemic.

Multiple events with the same PT which start on the same day are counted as only one occurrence.

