8.2.3.1. Study Holding Rules

Holding rules to be applied during the Study Intervention Administration Phase are presented in [Table 10](#). Meeting any of these holding rules will trigger a hold of study intervention irrespective of number of participants enrolled and/or timing of the event.

- Holding rules 1a-1d will be monitored by the investigators on a continuous basis throughout the study. Meeting any of these holding rules will trigger a hold of study intervention administration, irrespective of number of participants enrolled and/or timing of the event.

If an investigator detects one of the holding rules mentioned above, the study intervention administration will be immediately put on hold. GSK will be immediately informed and the data will be entered in the eCRF. It is GSK's responsibility to put the study intervention administration on hold at all sites.

- Holding rules will be assessed by the iSRC during safety evaluations on unblinded data. Meeting any of these holding rules will trigger a hold of study intervention administration.

Of note, no formal holding rules will be applied for other safety data such as non-life-threatening SAEs (those that are not meeting the definition of holding rule 1b), missed visits due to study intervention related AEs, Grade 1 and Grade 2 solicited and unsolicited AEs in the 7-day follow-up period and unsolicited AEs collected from 7 to 28 days after study intervention administration (refer to [Section 10.3.10.1](#) for assessment of intensity). However, to the extent of their availability, these data will also be reviewed by the SRT and iSRC to allow an overall assessment of the benefit/risk ratio of study intervention administration.

Table 10 Study Holding Rules

[figure not shown]
Holding Rule	Event	Number of Participants
1a	Death or any life-threatening SAE , regardless of causality	≥ 1
1b	Any non-life-threatening SAE that can be reasonably attributed to the study intervention administration	≥ 1
1c	Any withdrawal from the study (by investigator's or participant's request) and/or study intervention administration, following a Grade 3 AE	≥ 1
1d	Any solicited administration site or solicited systemic AE leading to hospitalization , or necrosis at the injection site, with an event onset within the 7-day (Days 1-7) post-study intervention administration period	≥ 1

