9.3.3. Primary Endpoints/Estimands Analyses

The analysis of the primary reactogenicity and safety objective will be performed on the ES.

Statistical Analysis Methods

The percentage of participants reporting at least one solicited AE, at least one solicited administration site AE, and at least one solicited systemic AE during the 7-day follow-up period (i.e., Day 1-Day 7 post-each study intervention administration) will be tabulated for each group after each dose and overall.
 
The percentage of participants reporting each individual solicited administration site AE (any grade and Grade 3) and solicited systemic AE (any grade and Grade 3) during the 7-day follow-up period (i.e., Day 1-Day 7 post-each study intervention administration) will be tabulated for each group after each dose and overall.
 
For solicited AEs, percentages will be computed based on the total number of solicited symptoms screens completed.
 
For each group and for each hematology and biochemistry parameter:
 
• The percentage of participants having hematology and biochemistry results below or above the laboratory normal ranges will be tabulated by timepoint.• The summary of grading post-study intervention administration will be tabulated vs. baseline. Grades will be based on the FDA Guidance for Industry “Toxicity Grading Scale for Healthy Adults and Adolescent Volunteers Enrolled in Preventive Vaccine Clinical Trials”; see Section 10.2.2). The laboratory parameters not included on FDA Toxicity Grading Scale will not be graded. 
The percentage of participants with any unsolicited AEs during the 28-day follow-up period (i.e., Day 1-Day 28 post-each study intervention administration) with its exact 95% CI will be tabulated by group and by MedDRA PTs. Similar tabulation will be done for Grade 3 unsolicited AEs, for any causally related unsolicited AEs, for Grade 3 causally related unsolicited AEs and for unsolicited AEs resulting in a medically attended visit. The verbatim reports of unsolicited AEs will be reviewed by a qualified person and the signs and symptoms will be coded according to the MedDRA Dictionary for Adverse Reaction Terminology. Every verbatim term will be matched with the appropriate PT.
 
For unsolicited AEs, percentages will be computed based on the total number of exposed participants. Participants not reporting an AE will be considered as not having experienced any AE.
 
The percentage of participants with any AEs (solicited and unsolicited) resulting in a medically attended visit from Dose 1 up to 28 days post last dose administered (Day 57, or Day 29 if only one dose administered) will also be tabulated by MedDRA SOC and PT by group, after each dose and overall with exact 95% CI.
 
The percentage of participants with at least one report of SAE, with at least one report of causally related SAE, with at least one report of fatal SAE, and with at least one report of causally related fatal SAE classified by the MedDRA SOC and PTs reported from Dose 1 up to 28 days post last dose administered (Day 57, or Day 29 if only one dose administered) will be tabulated by group with exact 95% CI.
 
The percentage of participants with at least one newly diagnosed pIMD and at least one exacerbation of a pre-existing pIMD classified by the MedDRA SOC and PTs and reported from Dose 1 up to 28 days post last dose administered (Day 57, or Day 29 if only one dose administered) will be tabulated by group with exact 95% CI.
 
The percentage of participants using concomitant medication (any medication, any antipyretic, and any antipyretic taken prophylactically, respectively) during the 7-day follow-up period (i.e., Day 1-Day 7 post-each study intervention administration) and during the 28-day follow-up period (i.e., Day 1-Day 28 post-each study intervention administration) will be summarized by group after each dose and overall.

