10.3.2. Definition of an SAE

An SAE is any untoward medical occurrence that:	
a. Results in death	
b. Is life-threatening	
Note: The term 'life-threatening' in the definition of 'serious' refers to an event in which the participant was at risk of death at the time of the event. It does not refer to an event, which hypothetically might have caused death, had it been more severe.

c. Requires hospitalization or prolongation of existing hospitalization	
Note: In general, hospitalization signifies that the participant has been admitted (usually involving at least an overnight stay) at the hospital or emergency ward for observation and/or treatment that would not have been appropriate in the physician's office or outpatient setting. Complications that occur during hospitalization are AEs. If a complication prolongs hospitalization or fulfills any other serious criteria, the event is serious. When in doubt as to whether "hospitalization" occurred or was necessary, the AE should be considered serious.

d. Results in disability/incapacity	
Note: The term disability means a substantial disruption of a person's ability to conduct normal life functions. This definition is not intended to include experiences of relatively minor medical significance such as uncomplicated headache, nausea, vomiting, diarrhea, influenza like illness, and accidental trauma (e.g. sprained ankle) which may interfere or prevent everyday life functions but do not constitute a substantial disruption.

e. Is a congenital anomaly/birth defect in the offspring of a study participant.	
f. Abnormal pregnancy outcomes (e.g. spontaneous abortion, fetal death, stillbirth, congenital anomalies, ectopic pregnancy).	
g. Other situations	

Medical or scientific judgment must be exercised in deciding whether reporting is appropriate in other situations. Important medical events that may not be immediately life-threatening or result in death or hospitalization but may jeopardize the participant or require medical or surgical intervention to prevent one of the other outcomes listed in the above definition should be considered serious. Examples of such events are invasive or malignant cancers; intensive treatment in an emergency room or at home for allergic bronchospasm; blood dyscrasias; and convulsions that do not result in hospitalization.

10.3.3. **Solicited events**

a. **Solicited administration site events**

The following administration site events will be solicited:

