### 1.1. Objectives, Estimands and Endpoints

Objectives	Endpoints and Estimands
Primary	
To evaluate the reactogenicity and safety of the HSVTI.	
 
Percentage of participants reporting each solicited administration site event (redness, pain, and swelling) within 7 days (Day 1-Day 7) post-each dose.
 
Percentage of participants reporting each solicited systemic event (fever, fatigue, headache, myalgia, arthralgia) within 7 days (Day 1-Day 7) post-each dose.
 
Percentage of participants reporting unsolicited AEs within 28 days (Day 1-Day 28) post-each dose.
 
Percentage of participants reporting MAEs from Dose 1 (Day 1) up to 28 days post-Dose 2 (Day 57).
 
Percentage of participants reporting SAEs from Dose 1 (Day 1) up to 28 days post-Dose 2 (Day 57).
 
Percentage of participants reporting newly diagnosed pIMDs from Dose 1 (Day 1) up to 28 days post-Dose 2 (Day 57).
 
Percentage of participants reporting exacerbation of pre-existing pIMDs from Dose 1 (Day 1) up to 28 days post-Dose 2 (Day 57).
 
Percentage of participants reporting any hematological and biochemical laboratory abnormalities at pre-study intervention administration (Day 1), post-Dose 1 (Day 8 and Day 29), and post-Dose 2 (Day 36 and Day 57).
 

Secondary	
To evaluate the humoral immune response induced by the HSVTI.	
 
CC1 antibody GMC and seropositivity rate (assessed by ELISA) at pre-study intervention administration (Day 1), 28 days post-Dose 1 (Day 29), and 28 days post-Dose 2 (Day 57).
 

To evaluate the cellular immune response induced by the HSVTI.	
 
Geometric mean of CC1 CD4+/CD8+ T-cells frequency expressing at least 2 activation markers (IFN-<math>\gamma</math>, TNF-<math>\alpha</math>, IL-2, IL-13, IL-17, 4-1BB and/or CD40L) and including at least one cytokine (assessed by CFC) at pre-study intervention administration (Day 1), 28 days post-Dose 1 (Day 29) and 28 days post-Dose 2 (Day 57).
 

To evaluate the safety of the HSVTI up to the end of follow-up period.	
 
Percentage of participants reporting MAEs from Dose 1 (Day 1) up to study end (Day 209).
 
Percentage of participants reporting SAEs from Dose 1 (Day 1) up to study end (Day 209).
 

Objectives	Endpoints and Estimands

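### In outputs that combine solicited and unsolicited AEs, SAP 6.2.3.7 would count a serious injection-site reaction as systemic only because a form lacks a field (minor)

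*SAP*

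**What the plan says.** SAP 6.2.3.7 opens by limiting its scope: "For output combining solicited and unsolicited AEs". Within that scope it gives two defaults.

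- For serious events: "all SAEs will be considered systemic events since the administration site flag is not included in the expedited AE eCRF pages".
- For the rest: "Unsolicited AEs with missing administration site flag will also be considered systemic".

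The reason given for the first default is a missing field on the form; no reason is given for the second. The readable SAP has no query, override or footnote for an event whose site is known from another source.

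Three other places bear on this:

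- Holding rule 1d (Protocol 8.2.3.1, Table 10) covers a solicited local or systemic event that puts the participant in hospital, "or necrosis at the injection site, with an event onset within the 7-day (Days 1-7) post-study intervention administration period".
- The SAE definition (Protocol 10.3.2) includes an event that "Requires hospitalization or prolongation of existing hospitalization".
- On coding of unsolicited events, Protocol 9.3.3 says: "Every verbatim term will be matched with the appropriate PT".

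**The concern.** The plan expects that a local reaction could be serious, since it wrote a holding rule for that case. Once such a reaction leads to hospital admission it is an SAE and goes onto the expedited pages. From then on a combined output treats it as systemic, even if its coded term names the injection site.

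The error runs in one direction. The section moves local events to the systemic side and has no rule that moves anything back. The SAP also treats this item differently from other missing items: under 6.2.3.9, missing severity, relationship or outcome of an unsolicited event is left unreplaced and shown as unknown. The site flag alone is filled in.

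The study is descriptive, with about 20, 20 and 10 participants, so single events shape the summaries. A combined table split by local and systemic could show an HSVTI formulation with a cleaner local profile, and a worse systemic one, than was observed.

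**Working it through.** The plan states no figure on this point, so there is none to reproduce. The check traces records through the rule, lists the outputs that use it, and sizes the effect of one event.

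**Inputs**
- Group sizes of about 20, 20 and 10: Protocol 6.3.3.
- Exact (Clopper-Pearson) 95% intervals for proportions: SAP 4.1.1.
- The two defaults and their scope: SAP 6.2.3.7.

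**Step 1. Illustrative records in a combined output**

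| Record | Route through the plan | Class under 6.2.3.7 |
|---|---|---|
| Injection-site redness, Day 3, hospitalized | SAE by the hospitalization criterion; expedited pages | Systemic |
| Injection-site necrosis, Day 5, hospitalized | Not a solicited event (Protocol Table 19 lists pain, redness, swelling); SAE by hospitalization | Systemic |
| Injection-site induration, non-serious, flag blank | Unsolicited; second default | Systemic |
| Injection-site induration, non-serious, flag marks the site | Unsolicited; neither default applies | Not affected |

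The first three are local events counted as systemic. Necrosis that is not serious and has a completed flag is not touched.

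**Step 2. Outputs that use the rule**

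| Output | Combines solicited and unsolicited? | Local/systemic rows described? |
|---|---|---|
| Solicited local endpoints (SAP 1.1; Protocol 9.3.3) | No | Solicited events only |
| SAEs (Protocol 9.3.3, 9.3.4) | Not stated | No; by SOC and PT |
| Medically attended AEs (Protocol 9.3.3, 9.3.4) | Yes | No; by SOC and PT |
| Main safety outputs (SAP 4.2) | Blacked out | Blacked out |

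The local primary endpoint reads "Percentage of participants reporting each solicited administration site event (redness, pain, and swelling) within 7 days (Day 1-Day 7) post-each dose", and its denominator is set separately: "For solicited AEs, percentages will be computed based on the total number of solicited symptoms screens completed". Neither uses 6.2.3.7. In a table by SOC and PT, an injection-site term stays visible whatever its class.

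**Step 3. Size of one reclassified event**

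Assume one participant in a group has a serious injection-site reaction and no other event in the local row. The exact limits are:
- x = 0: lower 0; upper = 1 − 0.025^(1/n).
- x = 1: lower = 1 − 0.975^(1/n); upper solves (1 − p)^n + n·p·(1 − p)^(n−1) = 0.025.

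For n = 20:
- x = 0: upper = 1 − 0.025^(1/20) = 16.8%.
- x = 1: lower = 1 − 0.975^(1/20) = 0.1%; upper = 24.9%.

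| Group | Local row under the rule | Local row if classed by site |
|---|---|---|
| HSVTI, n = 20 | 0/20 = 0% (0 to 16.8) | 1/20 = 5.0% (0.1 to 24.9) |
| Placebo, n = 10 | 0/10 = 0% (0 to 30.8) | 1/10 = 10.0% (0.3 to 44.5) |

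Two such participants in an HSVTI group would give 2/20 = 10.0% (1.2 to 31.7) in place of 0/20.

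The systemic row rises by one participant (1/20 = 5 points, or 1/10 = 10 points) only if that participant has no other systemic event. If a diary-recorded local event of the same participant is counted in the local row, the any-grade local count does not change.

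**Step 4. Chance that the case arises**

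The documents give no rate for serious injection-site reactions. Over assumed true rates p, the chance of at least one affected participant among the 40 HSVTI recipients is 1 − (1 − p)^40:
- p = 0.1%: 3.9%
- p = 1%: 33.1%
- p = 2%: 55.4%
- p = 5%: 87.1%

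**The case against.** The strongest reply is that no affected table can be shown. The only combined output in the readable text, medically attended AEs, is by SOC and PT, where a serious site reaction appears under its own term. The rule is pre-specified and applied identically to all groups, and no event is lost. Safety oversight does not depend on it: investigators monitor rule 1d continuously, and the internal safety committee reviews all accumulated unblinded safety data. All of this stands, and it is why the point is minor. It does not dispose of the point, because a rule that assigns a systemic class has a purpose only if some combined output uses that class.

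The size is also conditional. A serious reaction in the first week falls inside the diary window, so pain, redness or swelling may well be recorded too and hold the any-grade local count. This also stands. It would not prevent a false addition to the systemic row where the participant has no true systemic event.

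A third reply is that the preferred term need not name the site. The documents say only that verbatim terms are matched to preferred terms; cellulitis or necrosis could be coded without a location. That is right, and it is why the fix also uses the verbatim term and keeps a fallback.

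A reader might infer that the worst local reactions drop out of the primary reactogenicity results. The documents do not support that, because the solicited local endpoints are tabulated from solicited data alone. Nor does a blank flag mark a severe event: the second default catches non-serious events, and nothing suggests that blanks would be frequent or go unqueried.

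**Conclusion.** The point holds for combined outputs only. Followed as written, SAP 6.2.3.7 gives the wrong class to every serious administration-site reaction, and to every administration-site unsolicited event with a blank flag, in any combined output split by local and systemic.

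One such event moves the local row by up to 5 points in an HSVTI group or 10 points in placebo, always downwards, and the systemic row by up to the same amount upwards. This assumes groups of 20 and 10 and a participant with no other event in the row concerned. The number of events may be zero, and the number of affected tables cannot be checked because SAP 4.2 is blacked out in the public version. That is not a fault of the plan.

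The effect is one of presentation. There is no hypothesis test, and sample size, error rates, the SAE tables by SOC and PT and the holding rules are unchanged. Severity: minor.

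**What to change.** In SAP 6.2.3.7, replace the two defaults with a rule of this kind:

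- In combined outputs, classify an SAE, or an unsolicited AE with a missing site flag, as administration-site when its coded MedDRA preferred term names the administration site.
- Where the preferred term does not show the site, use the verbatim term, judged in a blinded review completed before the statistician is unblinded for the primary analysis. For events reported later, the review should be done by personnel who are still blinded.
- Count the event as systemic only where neither term indicates the site.
- Footnote the affected tables with the number of events classified in each way.

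The cost is a short amendment to one section, a short list of administration-site preferred terms, and a blinded review of a few events. No new data, eCRF change or additional procedure is needed. If the sponsor prefers to keep the defaults, a footnote on each combined local/systemic table naming any administration-site SAE counted as systemic would be the minimum.

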#### **6.2.3.8. Counting rules for occurrences of solicited events**

When the occurrences of solicited events are summarized, each event recorded as having occurred during a specific period will be counted as only one occurrence regardless of the number of days on which it occurs. Also, in the case of co-administered study interventions, an administration site event recorded for a participant following multiple study interventions will be counted as only one occurrence.

In addition, if a subject has multiple occurrences of a specific AE, data for each subject will be summarized according to the maximal severity observed during the follow-up period for each adverse event and each dose.

**Table 4 Intensity grading scale for solicited events**

Event	Intensity grade	Parameter
Pain at administration site	0	None
	1	Mild: Any pain neither interfering with nor preventing normal everyday activities.
	2	Moderate: Painful when limb is moved and interferes with everyday activities.
	3	Severe: Significant pain at rest. Prevents normal everyday activities.
Redness at administration site	0	< 25 mm
	1	25 - 50 mm
	2	51 - 100 mm
	3	> 100 mm
Swelling at administration site	0	< 25 mm
	1	25 - 50 mm
	2	51 - 100 mm
	3	> 100 mm
Temperature*	0	< 38.0°C (< 100.4°F)
	1	38.0°C (100.4°F) - 38.4°C (101.1°F)
	2	38.5°C (101.2°F) - 38.9°C (102.0°F)
	3	> 38.9°C (> 102.0°F)
Fatigue Headache Myalgia Arthralgia	0	None
	1	Mild: Symptom that is easily tolerated
	2	Moderate: Symptom that interferes with normal activity
	3	Severe: Symptom that prevents normal activity

\*The route for measuring temperature can be oral, axillary or tympanic. Fever is defined as temperature  $\geq 38.0^{\circ}\text{C}$  regardless of the location of measurement.

### 6.2.3.9. Counting rules for occurrence of unsolicited adverse events

Unsolicited AE summaries are including SAEs unless specified otherwise.

As per CDISC Vaccines Therapeutic Area guide, the solicited events which continue beyond the observation period are stored in the AEs domain but they do not contribute to the summaries of unsolicited AEs.

Missing severity, relationship with study intervention, and outcome of unsolicited AEs will not be replaced and will appear as 'UNKNOWN' when displayed in a statistical output.

